### **SENSITIVITY ANALYSIS:**

We will perform per-protocol sensitivity analyses on the primary outcome (change in VO2peak at 12 weeks) and secondary outcomes. To be included in these analyses, participants will need to have baseline and week 12 measurements for the outcome of interest and have completed >67% of the prescribed exercise intervention (“high” adherence, equivalent to 6 movement breaks per week, or 72 total exercise snacks)

Within-group changes from baseline for all outcomes will be reported as derived from the model employed for the primary (between-group) analyses outlined above

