### *Exercise adherence*

## Research Protocol

Self-reported adherence to the prescribed intervention will be determined using the automated weekly REDCap surveys. 9 exercise snacks or placebo exercises per week (equivalent to performing at least 3 per day on at least 3 days of the week) will be considered the minimum prescription. Participants completing 6 or more, 1-5, or 0 exercises will be classified as adherent, partially adherent, or non-adherent, respectively.

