### *Statistical Analysis*

Descriptive statistics will be calculated and data will be assessed for skewness and normality using Q-Q plots and Shapiro-Wilk tests (non-normal distributions will be log transformed as needed). The primary data analyses will be intention-to-treat. We will define feasibility of the exercise snacks intervention as >70% of participants completing at least 67%

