### BACKGROUND AND AIM:

From November 2022 to December 5, 2023, we completed the randomized clinical trial titled “Efficacy of Movement Breaks in Real-World Settings” at two study sites, McMaster University (Mac) and the University of British Columbia (UBC). The purpose of the study was to determine the efficacy of performing movement breaks as either vigorous-intensity “exercise snacks” (ES) or low-intensity mobility-based control activities (CTL) on indices of cardiometabolic health. All movement breaks involved ≤60-second bouts of activity performed periodically throughout the day. Participants in both groups were given access to a web platform that provided individualized notifications to remind them to complete their ES or CTL bouts at least 3 times per day on at least 3 days per week (i.e., minimum prescription of 9 movement breaks per week). Identical scripted counselling at baseline, week 4, and week 8 assisted with individualization and progression of the two movement break prescriptions. Exercise prescription progression and variety were accomplished by altering the exercises in weeks 1-4 (Phase 1), weeks 5-8 (Phase 2), and weeks 9-12 (Phase 3). The primary outcome measure was change from baseline in cardiorespiratory fitness (CRF; assessed via cycling VO2peak test) following the 12-week exercise intervention. Secondary outcomes included changes in basic anthropometric measures (body mass and waist circumference); fasting plasma insulin, glucose, homeostasis model assessment of insulin resistance (HOMA-IR), and inflammatory cytokines; device-measured and self-reported adherence to movement breaks; and enjoyment and perceived exertion following movement breaks. It was hypothesized that a 12-week technology-enabled real-world ES intervention would improve CRF as compared to CTL in previously inactive adults.

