**Secondary outcome measures:** To supplement the primary outcome of VO2peak in mL/kg/min we will also analyze peak power output and absolute VO2peak (L/min). Key secondary outcomes will include exercise adherence, enjoyment, and perceived exertion assessed by self-report. Self-reported adherence to the intervention will be determined by user analytics on the Seven Movements platform and using the automated weekly REDCap surveys. We will define high, moderate, or low adherence as completing >67%, 50-66% or <50% of the prescribed intervention (i.e., total # of snacks performed relative to minimum prescription of 9 snacks per week and the number of days when participants completed  $\geq 3$  snacks relative to a prescription of 3 days per week). Enjoyment (Exercise Enjoyment Scale) and perceived exertion (Borg CR-10 scale) will be asked following each snack. Adherence, enjoyment, and exertion data will be analyzed using a linear mixed model that will include fixed effects for group (ES vs. CTL), timepoint (week, Phase or session number), their interaction, and stratified allocation factors (site, sex) and random effects for participants. In these analyses, the main effect of group will be most important to identify an overall effect of the intervention on these variables.

Other continuous secondary outcomes assessed at baseline and a follow-up timepoint will be analyzed similarly to the primary outcome using a constrained baseline longitudinal data analysis linear mixed model (with all relevant follow-up timepoints included as a fixed factor of time in the model). Secondary outcomes include:

- Changes in anthropometrics assessed at baseline and 12-weeks.
- Changes in blood markers (fasting plasma glucose, insulin, HOMA-IR, inflammatory cytokines) assessed at baseline and 12 weeks.

- Changes in hematology analysis of complete blood count (total white blood cells, hematocrit, hemoglobin, monocytes, neutrophils) assessed at baseline and 12-weeks.
- Changes in device-worn physical activity and sedentary time assessed at baseline, week 2, and week 11 via device-worn measurement.
- Changes in leisure time physical activity assessed by GLTEQ measured at baseline and 12 weeks.

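### The SAP's per-protocol cut-off of >67% excludes the 12-week total it is said to equal (72 of 108), and the adherence bands leave that total in no category

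*SAP*

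**What the plan says.** The SAP (Background and Aim) asks for movement breaks "at least 3 times per day on at least 3 days per week (i.e., minimum prescription of 9 movement breaks per week", and places the primary outcome assessment "following the 12-week exercise intervention".

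The SAP's text on secondary outcome measures sets three bands: "We will define high, moderate, or low adherence as completing >67%, 50-66% or <50% of the prescribed intervention". It measures completion in two ways. One is "total # of snacks performed relative to minimum prescription of 9 snacks per week"; the other is the number of days with three or more snacks, against three such days a week.

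The SAP's Sensitivity Analysis section then defines the per-protocol set for the primary and secondary outcomes. Participants must have the baseline and week 12 measurements and "have completed >67% of the prescribed exercise intervention". The section labels this high adherence and describes it as "equivalent to 6 movement breaks per week, or 72 total exercise snacks".

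The protocol uses the same level inclusively, for other purposes. Under Exercise adherence: "Participants completing 6 or more, 1-5, or 0 exercises will be classified as adherent, partially adherent, or non-adherent, respectively". Under Statistical Analysis: "We will define feasibility of the exercise snacks intervention as >70% of participants completing at least 67" per cent of the prescription, which it explains as 6 snacks a week, in at least 9 of the 12 weeks.

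**The concern.** The per-protocol rule is given both as a percentage and as a count, and the two give different answers at the value the SAP names. Someone with 72 snacks reaches the stated count but fails the stated percentage. Whoever writes the code must choose, and the text does not settle the choice.

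The bands share the problem because they run from 50-66% straight to >67%, with nothing in between. The level that falls in the gap is two-thirds of the prescription, which is the level the SAP uses as its benchmark for high adherence.

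At stake are membership of the per-protocol set, for the primary and the secondary outcomes, and the classification of adherence, which the SAP lists among its key secondary outcomes.

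**Working it through.** **Inputs**
- Minimum prescription: 9 per week (SAP, Background and Aim; Secondary outcome measures).
- Duration: 12 weeks (SAP, Background and Aim).
- Per-protocol cut-off: >67%, said to equal 6 per week or 72 in total (SAP, Sensitivity Analysis).
- Bands: high >67%, moderate 50-66%, low <50% (SAP, Secondary outcome measures).
- Days measure: 3 per week (same place).

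**Step 1: reproduce the SAP's count.** 6 × 12 = 72. The count is right as a 12-week total.

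**Step 2: turn the count into a percentage.** Prescribed total = 9 × 12 = 108. Then 72/108 = 6/9 = 66.67%, which is not above 67%.

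**Step 3: turn the percentage into a count.** 0.67 × 108 = 72.36, so the smallest whole number that passes >67% is 73 (73/108 = 67.59%).

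**Step 4: apply the bands to 12-week totals.** The upper edge of moderate is 0.66 × 108 = 71.28, so the last moderate total is 71. The lower edge is 0.50 × 108 = 54.

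| Total | % of 108 | Band as written |
|---|---|---|
| 53 | 49.07 | low |
| 54 | 50.00 | moderate |
| 71 | 65.74 | moderate |
| 72 | 66.67 | none |
| 73 | 67.59 | high |

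Over all totals from 0 to 108, 72 is the only one without a band. Totals above 108 exceed 100% and are high.

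**Step 5: does rounding close the gap?** No. To a whole per cent, 66.67% becomes 67%, which is neither >67% nor within 50-66%. To one decimal it becomes 66.7%, with the same result.

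**Step 6: smallest total admitted under each possible coding**

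| Coding | Smallest total admitted |
|---|---|
| >67%, unrounded or rounded to a whole per cent | 73 |
| ≥67%, unrounded | 73 |
| ≥67%, rounded to a whole per cent | 72 |
| ≥ two-thirds | 72 |

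Replacing > with ≥ therefore works only if percentages are rounded first.

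**Step 7: the same gap on other scales.** For days, 3 × 12 = 36 and 24/36 = 66.67%, the only unclassified value. For a single week, 6/9 = 66.67% is unclassified, while 5/9 = 55.56% is moderate and 7/9 = 77.78% is high. The SAP does not say that the bands are applied week by week; if they were, every week with exactly 6 breaks would have no label.

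**The case against.** The arithmetic is not in dispute, but four points can be made against the concern.

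1. **The per-protocol sentence may be consistent with itself.** It does not say that 72 or more qualifies. If 67% is two-thirds rounded and 72 is the boundary, more than 67% and more than 72 both start at 73. This reading is possible, but it fits poorly with a gloss that presents 6 per week as what high adherence means, and it leaves 72 without a band.

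2. **The inclusive intent is borrowed.** The protocol passages that include the boundary define weekly adherence and feasibility, not the SAP's per-protocol set. This stands as a limit: they make the inclusive reading more likely but do not prove it. A strict rule, with high from 73 and moderate 54 to 72, would also close the gap, so the authors should confirm which they meant.

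3. **The consequence is very small.** The primary analysis is intention-to-treat, adherence is analysed with a linear mixed model, and the dose-response analysis uses the number of snacks rather than the bands. This stands, and it limits the weight of the point.

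4. **Other parts of the rule are also open.** The per-protocol sentence does not say whether platform records or weekly surveys supply the count, whether the days measure counts, or how missed surveys affect the denominator. On 11 reported weeks, for example, the denominator would be 9 × 11 = 99 and two-thirds would be 66. These are separate gaps. They show that the figure of 72 depends on a fixed denominator of 108, but they do not remove the inconsistency.

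**Conclusion.** The concern holds. As written, the percentage rule first admits 73, although the SAP equates it with 72, and the bands give 72 no category under any of the roundings checked. The source of the error is a strict inequality combined with two-thirds rounded up to 67%.

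The impact is minor. With completion taken as the 12-week total over 108, only participants with exactly 72 snacks change status (or exactly 24 qualifying days, if days are banded). The documents do not give the number of such participants, and it may be zero. The per-protocol sensitivity analyses and the adherence classes are affected; the intention-to-treat primary analysis is not. The point is still worth correcting, because the rule defines an analysis set and is ambiguous at its own benchmark.

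**What to change.** State the thresholds as counts, or as the exact fraction two-thirds:

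- **High:** at least 72 of 108 snacks over 12 weeks (an average of at least 6 per week).
- **Moderate:** 54 to 71.
- **Low:** fewer than 54.
- **Per-protocol entry:** total of at least 72, in addition to the required baseline and week 12 measurements.

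If the days measure is banded too, use the same boundaries: at least 24 of 36, 18 to 23, fewer than 18. Every possible value then falls in exactly one class.

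In the code, change the constant as well as the operator (two-thirds in place of 0.67), or test the total against 72 directly.

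The cost is one sentence in the SAP's secondary outcomes text and one in its Sensitivity Analysis section, with no new data. On 12-week totals the per-protocol set can only gain participants with exactly 72. The SAP reports the trial as completed by December 5, 2023 and plans for the analysis to be blinded to allocation, so the change should be recorded as a dated clarification while that blinding holds. If that is no longer possible, report the per-protocol results under both codings (72 or more, and more than 72).

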### **EXPLORATORY ANALYSES:**

Dose-response analyses exploring whether the number of completed exercise snacks (recorded in the Seven Movements platform and in weekly self-report surveys) and/or differences in RPE (i.e., “intensity”) during exercise snacks are associated with changes in key outcomes

## HANDLING OF MISSING DATA AND OTHER DATA CONVENTIONS

No statistical imputations will replace missing data for the outcome measures (data as observed). However, the constrained baseline longitudinal data analysis – in a linear mixed model with restricted maximum likelihood – is a principled approach to addressing missing outcome data, including the baseline value of the continuous outcome measure. The model permits the inclusion of all participants in the analysis with either a baseline or a follow-up value. Thus, missing data will not be imputed for the ITT analyses. If a blood marker value is below the detection limit, we will explore the results following imputation of the value as limit of detection (LOD) divided by the square root of 2 (6).

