## Research Protocol

increases in heart rate and CRF. We selected this as the most appropriate control group in attempts to balance randomization expectations, retention, and ethical considerations compared to a true “hands off” or “no exercise” control.

Technology – Participants will be able to log the timing, duration, and number of exercise snacks completed daily as well as the perceived effort (Borg CR-10 scale) and enjoyment (Exercise Enjoyment Scale) of each snack into the platform. Participants will also be sent weekly self-report adherence surveys via email RedCap link wherein adherence will be assessed by asking participants the total number of snacks completed each week. If participants miss the weekly adherence self-assessment, we will follow-up with an email reminder and (if necessary) a follow-up telephone call to help address any concerns/issues that may have prevented them from completing the weekly assessment. To characterize exercise adherence and track changes in daily physical activity, sedentary time, and sleep patterns, we will provide participants with validated thigh-worn triaxial accelerometers (activPAL4) in line with our previous work. Accelerometer data will be obtained during two, separate 7-day periods (intervention weeks 2 and 11) and extrapolated to the rest of the intervention. As exercise adherence generally diminishes over an intervention, obtaining this data during both early and late stages of the intervention will provide valuable information relating to changes in adherence over the intervention.

Virtual check-ins: To help participants complete their customized movement break plan and to address any potential barriers/challenges that you may encounter of the course of the intervention, we will conduct virtual (phone or zoom) sessions at the 4 and 8 week point of the

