### A PRIORI SAMPLE SIZE CONSIDERATIONS

A sample size of 30 participants per group was deemed sufficient to detect a within-between interaction with a medium effect size (Cohen's  $f=0.25$ ,  $d=0.50$ ) for the primary outcome (CRF) assuming 90% power with a two-tailed  $\alpha$  set at 0.05 (G\*Power v3.1). This effect size equates to ~1 metabolic equivalent (MET) increase in CRF (assuming a mean baseline VO2peak of 30-35 mL/kg/min with a SD of 5-7 mL/kg/min[4-9]). The grant was funded by the Canadian Cancer Society Action Grant special call for interventions designed for primary cancer prevention. A 1-MET increase in CRF was deemed clinically relevant for primary cancer prevention based on epidemiological data showing 10-21% decrease in cancer incidence for each 1 MET increase in CRF[1-2]. To preserve power and account for a 20-30% dropout rate, we aimed to recruit 40 participants per group (80 participants total; equal sex distribution). Randomization was stratified based on study site (i.e., Mac or UBC) and participant sex (i.e., male or female). These calculations were documented in the original grant application (Feb 2021), trial protocol (Oct 6, 2022), and SAP (V1 June 2023).

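### Under the SAP's no-imputation rule, mean weekly adherence describes participants who are still reporting, not everyone randomised

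*SAP*

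**What the plan says.** The SAP section on handling of missing data states "No statistical imputations will replace missing data for the outcome measures (data as observed". Its only exception is blood markers below the detection limit.

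Under secondary outcome measures, the SAP says "Key secondary outcomes will include exercise adherence, enjoyment, and perceived exertion assessed by self-report". It continues: "Adherence, enjoyment, and exertion data will be analyzed using a linear mixed model". The model has group, timepoint, their interaction, the stratification factors and a random participant effect, and "the main effect of group will be most important to identify an overall effect of the intervention on these variables". The adherence percentage is the "total # of snacks performed relative to minimum prescription of 9 snacks per week", with no number of weeks given at that point. The SAP's sensitivity analysis section equates high adherence with 6 breaks per week or 72 in total. Two sources feed adherence: the weekly REDCap survey and the Seven Movements platform count.

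The Protocol (Step 5, Technology) follows a missed survey with an email and, if needed, a call. It gives no rule for a survey that stays missing. The same section expects decline over time: "As exercise adherence generally diminishes over an intervention". The Protocol's statistical analysis section states: "We will define feasibility of the exercise snacks intervention as >70% of participants completing at least 67" per cent of the minimum, spelled out as 6 snacks a week, in at least 9 of 12 weeks. The SAP does not repeat this criterion. Its sample size section plans recruitment as follows: "To preserve power and account for a 20-30% dropout rate".

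**The concern.** For VO2peak, a missing value is a measurement that exists but was not taken, and leaving it to a likelihood-based model is defensible under missing at random. Weekly adherence is different. A participant who has stopped has, in most cases, done no breaks that week, so the reason for the gap is itself the outcome. The mixed model in effect projects that person's earlier, active weeks forward. The resulting mean describes adherence while people were still reporting, whereas a reader will take it as uptake among those randomised.

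Adherence is central to the Protocol's aim, which pairs feasibility with efficacy. The SAP also compares the arms on it, and that comparison can be distorted if one arm loses more people than the other.

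**Working it through.** **1. The SAP's own adherence figure.** 6 per week × 12 weeks = 72, and the minimum prescription is 9 × 12 = 108. 72/108 = 66.7%, so the 72 reproduces on a full 12-week frame. It falls just short of the stated cut-off of more than 67%, since 0.67 × 108 = 72.36.

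**2. Size of the effect on an arm mean.** From the documents: 12 weeks, a minimum of 9 breaks per week, dropout *d* of 20-30%. Assumed: 9 breaks per week while active, none after stopping, and dropouts losing a share *m* of the 12 weeks. The mean with zeros is 9 × (1 − *d·m*). The as-observed mean stays at 9, so the overstatement ratio is 1/(1 − *d·m*).

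| Dropout | *m* = 25% | *m* = 50% | *m* = 75% |
|---|---|---|---|
| 20% | 8.55 (+5.3%) | 8.10 (+11.1%) | 7.65 (+17.6%) |
| 25% | 8.44 (+6.7%) | 7.88 (+14.3%) | 7.31 (+23.1%) |
| 30% | 8.33 (+8.1%) | 7.65 (+17.6%) | 6.98 (+29.0%) |

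Each cell gives the zero-filled mean per week and, in brackets, the excess of the as-observed mean over it.

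A second set of assumptions has completers at 8 per week and dropouts at 6 per week until they stop, on average after week 5. At 20% dropout the as-observed mean is 0.8 × 8 + 0.2 × 6 = 7.60, against 0.8 × 8 + 0.2 × 6 × 5/12 = 6.90 with zeros (+10%). At 30% it is 0.7 × 8 + 0.3 × 6 = 7.40, against 0.7 × 8 + 0.3 × 6 × 5/12 = 6.35 (+17%). Both lie inside the range above.

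**3. Check with a fitted mixed model.** Simulation with 100 runs, 40 per arm and 12 weeks. Both arms have a true mean of 9 per week while active, between- and within-person SD are 2, and dropouts stop after weeks 2 to 10 (all assumed).

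| Dropout, snacks / control | Snacks mean: as observed, zeros | Group difference: as observed, zeros |
|---|---|---|
| 25% / 25% | 9.04, 7.93 | +0.07, +0.09 |
| 30% / 20% | 9.03, 7.69 | +0.05, −0.42 |
| 20% / 30% | 8.98, 8.10 | +0.05, +0.59 |

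The as-observed differences are noise around zero. With equal dropout the group effect hardly changes. With unequal dropout it shifts by roughly half a break per week, and the sign depends on which arm loses more.

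**4. Feasibility criterion.** This is a count for each participant: at least 6 snacks in at least 9 of 12 weeks. Someone who stops after week 8 has at most 8 qualifying weeks and fails, whatever the mixed model does. What can move the result is who counts as a participant:
- All 40 randomised to snacks: 0.70 × 40 = 28, so more than 70% needs 29.
- With 25% dropouts removed, 30 remain: 0.70 × 30 = 21, so 22 suffice, and 22/40 = 55% of those randomised.

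**5. Adherence percentage.** A participant doing 9 per week who stops after week 6 scores 54/54 = 100% (high) over reported weeks, but 54/108 = 50% (moderate) over 12 weeks. The 72-break figure points to the second reading, but the definition of the percentage does not say so.

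**The case against.** The strongest reply is that neither document says how unreturned weekly surveys are handled. The missing-data section mainly explains the constrained-baseline model, and adherence has no baseline survey count and gets a different model. That is fair as a description of emphasis. But the rule is worded for the outcome measures in general, excepts only blood markers, and adherence is named as an outcome. Following the plan as written leaves those weeks missing.

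A reader might infer more: that the rule inflates the feasibility result itself. The documents do not support this. The criterion and the 72-break threshold use a fixed 12-week frame, in which an unreported week adds nothing. One can also work out that 20%, 25% or 30% dropout would require 87.5%, 93.3% or 100% of completers to reach 70% of all randomised (0.70/(1 − *d*)). That arithmetic concerns the denominator of people and assumes every dropout fails; it does not follow from the missing-data rule. Nor do the documents say that dropouts leave that denominator. The Protocol mentions intention-to-treat just before defining feasibility, although the SAP's full analysis set is worded for the primary outcome.

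Three further points stand. The platform log is a second source in which inactivity naturally reads as zero, but the SAP does not say which source governs. The 20-30% dropout is a power allowance for VO2peak, and someone who misses the final test may have kept exercising. And an unreturned survey does not prove that nothing was done, so scoring every such week as 0 in the main analysis would bring its own bias.

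**Conclusion.** The concern holds for the mixed-model means of weekly self-reported breaks. They estimate adherence while still reporting, and they are too high in each arm if stopping means few or no breaks. The excess is about 5-29% relative to the zero-filled mean, or 14% at 25% dropout with half the weeks lost. Only the 20-30% dropout range comes from the documents; the weekly rate, the stopping times and the equation of dropout with stopping are assumptions, so these figures show scale and are not a forecast.

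The main effect of group has no fixed direction of bias. It is little affected when dropout is similar in the two arms and can move either way when it is not.

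It would go too far to say that the rule favours a finding of feasibility. Feasibility would be overstated only if dropouts were left out of the denominator or the weeks were rescaled, and the documents leave this open without stating either. The primary VO2peak analysis is not affected.

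**What to change.** In the SAP's secondary outcome and missing-data sections, exempt adherence from the as-observed rule and state that:
- weeks after a documented withdrawal or stop count as 0;
- for an unreturned survey without a documented stop, the Seven Movements platform count is used where available;
- adherence percentages are taken over 12 weeks (108 breaks);
- these percentages and the feasibility proportion use all randomised participants in the relevant arm, and the Protocol's feasibility criterion is restated in the SAP;
- two sensitivity analyses are reported: the as-observed mixed model, and a version scoring all remaining unreported weeks as 0.

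The cost is SAP wording and a re-run on data already collected. The downside is that reported adherence will be somewhat lower.
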